2.1.1 General definitions

Study drug

Novartis will supply the investigational product listed below

- AMG 334 70 mg/1 mL pre-filled syringe
- Matching placebo in 1mL pre-filled syringe, identical in appearance

Two injections of AMG 334 70 mg (equaling 140 mg total dose) or placebo will be administered at each dosing visit. The matching Placebo to AMG 334 pre-filled syringe will have the same appearance as the investigational drug. Each syringe will be packaged individually in double blinded fashion for the double-blind treatment Epoch. The study treatments will be labelled as:

- AMG 334 70mg/1mL or Placebo for Double-Blind Treatment Epoch

Baseline

The baseline period for efficacy endpoints collected by the daily diary (e.g., monthly migraine days, acute migraine-specific medication days, MPFID, etc.) is defined as the period

between week -4 visit (when eDiary device is dispensed to the patient for daily data capture) and the day prior to study day 1 (study day 1 is not included).

A baseline for PRO ([REDACTED] MPFID) and safety (including C-SSRS) values refers to the last evaluable measurement prior to the first administration of the study drug, irrespective of re-screening. In this case, baseline values will be the values obtained on the day of the randomization (Day 1, Visit 101), or on an earlier visit (scheduled or unscheduled) which is the closest to Visit 101, if Visit 101 is missing or the assessment was not done at baseline.

Change from Baseline in Monthly Efficacy Measurement

The change from baseline in monthly efficacy measurement is the monthly efficacy measurement in the monthly interval prior to the given time point minus the baseline monthly efficacy measurement. Please, refer to the monthly intervals for efficacy endpoints defined in [Table 2](#). For example, change from baseline in monthly migraine days in the last month (month 3) of the double-blind epoch will be calculated based on the following:
(Monthly migraine days in the last month of the DBTE) – (monthly migraine days during the baseline phase)

If the baseline or post-baseline value is missing, then the change from baseline is set to be missing.

Percent Change from Baseline

The change from baseline divided by baseline and multiplied by 100:

$$(\text{post-baseline} - \text{baseline}) * 100 / \text{baseline}$$

50% (or 75%, 100%) response is defined as a decrease from baseline score value for at least 50% (or 75%, 100%).

Study day

Study Day 1 is defined as the first investigational product (IP) dose date. For subjects who are randomized but not dosed after randomization, the Study Day 1 is defined as the date of randomization.

Study Day is defined as the number of days from Study Day 1.

Before Study Day 1:

$$\text{Study Day} = (\text{Date of Interest} - \text{Date of Study Day 1})$$

On or after Study Day 1:

$$\text{Study Day} = (\text{Date of Interest} - \text{Date of Study Day 1}) + 1$$

Therefore the day prior to Study Day 1 is -1.

Last date of patient contact

The date of last patient contact will be selected as the minimum of the following non-missing dates:

1. 'Date of Discontinuation/study phase completion', either from the study completion page or
2. The treatment epoch completion page if calculated specifically for a study epoch.

Duration of Migraine

The duration of migraine in years (migraine with aura or migraine without aura, whichever is earlier) is calculated by the following formula: current age (in years) - age at migraine onset (in years).

Current age is calculated by the following formula, the date of informed consent – birth date (at least the year).

If the current age calculated as detailed above or the age at migraine onset is missing then duration of migraine will be missing.

Duration of exposure to AMG 334

For all calculations of exposure, dose date refers to receiving dose > 0, but can include partial doses.

Duration of DB IP Exposure

If subject enters into the open-label treatment phase,

Duration = Minimum (Last DB Dose Date + 27, First OLTP Dose Date, EoS Date-1) – First DB Dose Date+1

Otherwise,

Minimum (Last DB Dose Date + 27, EoS Date) – First DB Dose Date+1

Duration of OL IP Exposure

Minimum (Last OLTE Dose Date + 27, EoS Date) – First OLTE Dose Date+1

Subject Incidence

The subject incidence for a given event in a given period is defined as the number of subjects with at least one reported occurrence of the event divided by the number of subjects who entered that period. For subjects with multiple occurrences of the same event, the event will only be counted once per subject.

Exposure-Adjusted Subject Incidence Rate

The exposure- adjusted subject incidence rate for a given event in a given period is defined as the number of subjects with at least one reported occurrence of the event in a given time period divided by total subject years at risk in that period. The time at risk for each subject will differ for each adverse event. For subjects with events, only the time until the first event contributes to the total subject years at risk. For subjects who do not experience the event, the time at risk will be calculated based on the safety analysis study window. This rate will be presented per 100 subject years. For subjects with multiple occurrences of the same event, the event will be only counted once per subject.

Time at risk

The time at risk matches the time generally considered for safety summaries except SAEs. In particular, it will be used in the analysis of adverse events to derive (exposure-adjusted) incidence rates.

Prior and concomitant medication

Prior medication will be defined as any non-study medication taken prior to the first dose of the randomized study medication, irrespective of whether the medication continued into the treatment period.

Any non-study medication administered at least once between the day of first dose of randomized study medication and end of the study will be a concomitant medication.

Analysis windows

In general, by-visit analyses, including evaluable scheduled and unscheduled data, will be conducted using analysis windows. Analysis windows will align with the scheduled visit day for each assessment and have its lower and upper bounds symmetrically between the analysis window midpoints (i.e. the scheduled visit day for the particular assessment).

For efficacy parameters: In case of multiple assessments within a analysis window, the scheduled visit will be used regardless of the distance from the target day. Unscheduled visit will only be used when there is no measurement from the scheduled visit in the defined window. In that case the assessment value closest to the scheduled visit day will be used. In case of equal distances, the latest assessment value will be used. The exception is an assessment at early study withdrawal visits along with another assessment within a window. In such cases the early-withdrawal assessment will be used.

For safety parameters: in case of competing assessments within a analysis window, the last one closest to the scheduled visit day will be used.

Listings will include all assessments, sorted by scheduled visit and time of assessment, flagging unscheduled visits. The listings will include analysis windows and corresponding flags to indicate the assessment's inclusion in analysis.

Further details regarding analysis windows for specific domains are included in Tables below.

Monthly Interval for Efficacy Endpoints

Monthly efficacy measurements will be calculated based on the subject's monthly investigational product(IP) dosing schedule defined below using eDiary data collected from beginning of the baseline phase (week -4 visit) up to open label treatment period.

Table 2 Study Intervals for Efficacy Endpoints

Study Phase	Assessment Timepoint	Interval Based on Dose Dates	
		Start date	End date
Baseline Epoch	Baseline	From eDiary device assignment date (or Week -4 visit)	Day prior to study day 1
Double-Blind Treatment Epoch	Week 4	Study Day 1	
 • Week 4 dose date-1 • Study day 28 if Week 4 dose is not received (either missed or IP discontinued prior to Week 4) 
Note: if day 1 dose is the last IP dose subject received, the rest of monthly rates during DBTE will be calculated based on consecutive 28-day interval beginning on study day 29 (ie, 29-56 for week 8, 57-84 for week 12)

	Week 8	
 • Week 4 dose date 
Study day 29 if Week 4 dose is not received (either missed or IP discontinued prior to Week 4)
	
 • Week 8 dose date-1 
Study day 56 if Week 8 dose is not received (either missed or IP discontinued prior to Week 8)

	Week 12	
 • Week 8 dose date 
Study day 57 if Week 8 dose is not received (either missed or IP discontinued prior to Week 8)
	
 • Week 12 IP dose date-1 • If Week 12 dose is not received (either missed or IP discontinued prior to Week 12) 
 ○ MIN (Study day 84, EOS) if Week 8 dose is not received ○ MIN (Week 8 dose date + 27, EOS) if week 8 dose is

			received
--	--	--	----------

Study Visit

Since the actual visit for a subject may not exactly coincide with their targeted visit date, the actual visit date is mapped to a study visit.

The next study day window will be utilized to define study visit for lab, vital signs, C-SSRS and some PROs collected during office visits [REDACTED] before dose is administered [REDACTED]

Table 3 Study Visit Windows

Study visit	Target Day	Study Day for vital signs, C-SSRS (for lab [REDACTED] include only Day1, Week 12, 24, 64)	Study Day [REDACTED]
Baseline	Please refer to Section 2.1.1		
Day 1	1	1	1
Week 4	29	16-43	16-43
Week 8	57	44-71	44-71
Week 12	85	1.72 to (week 12 OLTE dose date) for subjects who receive OLTE dose at week 12 2.72-99 for subjects who did not receive OLTE dose at week 12	1.72 to (week 12 OLTE dose date) for subjects who receive OLTE dose at week 12 2.72-99 for subjects who did not receive OLTE dose at week 12

For safety analyses which are summarized by study phase, analysis windows will be set up based on study phase:

Table 4 Study Phases for Safety analysis

Study Phase	Start Time Point	End Time Point
Double-blind Treatment Epoch	Study Day 1 (after the 1st DB IP Dose)	
 • First OLTE Dose Date - 1 for subjects receive OLTE IP dose; • MIN(EoS Date, last IP dose date + 84 days) for subjects did not receive any OLTE IP dose

Note: all anti-AMG 334 antibody data during all epochs will be included in immunogenicity analysis.

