5.5.4 Instructions for prescribing and taking study treatment

Subcutaneous (s.c.) injections are to be given for each investigational product administration. For purposes of study treatment dosing, “q.m.” refers to an every 4 weeks injection regimen. The study drug administration date should be in 4 week increments (+/- 5 days) from the first dose of study drug. Any dose administrations that may occur greater than +/- 5 days from the 4 week time point (e.g., patient unavailability) should be discussed with the Sponsor prior to dosing. The anatomical sites for administration of investigational product are the upper arm, upper thigh, or abdomen; the location of the injection sites should be documented in the source document.

Double-Blind Treatment Epoch:

Two injections of AMG 334 70 mg (equaling 140 mg total dose) or placebo will be administered by qualified study staff at each dosing visit during the 12-week double-blind treatment epoch (i.e., at Day 1 and Weeks 4 and 8).

Open-label Treatment Epoch and PTA-Open-Label Treatment Epoch:

Two injections of open-label AMG 334 70 mg (equaling 140 mg total dose) will be administered by qualified study staff at each dosing visit during the 156-week open-label treatment epoch (ie, at Weeks 12, 16, 20, 24, etc.) and during the PTA-Open-Label Treatment Epoch (ie, at Weeks 168, 172, 176, 180 etc.). If and when 140 mg/mL pre-filled syringes become available during the Open-Label Treatment Epoch, the 140 mg dose may be administered by a single 140 mg/mL s.c. injection.

The investigational product dose is fixed and will not be adjusted for individual patients during the study. There are no temporal restrictions for study drug administration (e.g., proximity to meals, sleep or activity).

All kits of study treatment assigned will be recorded in the IRT. Novartis monitors will reconcile treatment assigned vs treatment administered and ensure that the information is congruent during their monitoring visits.

During the **COVID-19 pandemic** that limits or prevents on-site study visits, delivery of study drug directly to a patient’s home is generally permitted in the event the Investigator has decided that an on-site visit by the patient is no longer appropriate or possible, and that it is in the interest of the patient’s health to administer (e.g., self-injection or study staff administration at patients’

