2.4 Treatments (study treatment, rescue medication, concomitant therapies, compliance)

2.4.1 Study treatment / compliance

Subcutaneous (sc) injections are to be given for each investigational product administration. For purposes of study treatment dosing, “qm” refers to an every 4 weeks injection regimen.

Double-Blind Treatment Epoch:

AMG 334 140 mg or placebo will be administered by qualified study staff at the each dosing visit during the 12-week double-blind treatment epoch (ie, at Day 1 and Weeks 4 and 8).

Study medication is administered by the investigator or designated study staff at each visit. This information should be captured in the source document and the eCRF at each visit. All

study treatment dispensed and returned must be recorded in the Drug Accountability Log. Site staff will review eDiary compliance with the patient at each visit.

Compliance:

Compliance to eDairy at each month is calculated as:

1. (Number of observed eDairy days at baseline or between IP doses/ 28)*100% if Number of actual days in Baseline epoch or between IP doses interval ≤ 28 or
2. (Number of observed eDairy days at baseline or between IP doses/ Number of actual days in Baseline epoch or between IP doses interval)*100% if Number of actual days in Baseline epoch or between IP doses interval > 28 .

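### SAP 2.1.1: for patients who enter open label, double-blind exposure runs through the first open-label dose date, so that day is counted in both epochs when the two doses are 27 days or fewer apart

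*SAP*

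**What the plan says.** SAP 2.1.1 (General definitions) gives three exposure formulas.

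- Double-blind, patients who enter open label: the end date is "Duration = Minimum (Last DB Dose Date + 27, First OLTP Dose Date, EoS Date-1"). The first double-blind dose date is subtracted and 1 is added. OLTP is read here as the same period that the section otherwise calls OLTE.
- Double-blind, all other patients: "Minimum (Last DB Dose Date + 27, EoS Date) – First DB Dose Date+1".
- Open label: "Minimum (Last OLTE Dose Date + 27, EoS Date) – First OLTE Dose Date+1".

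Two other rules in the same section draw a boundary at the first open-label dose. Table 4 ends the double-blind safety phase at "First OLTE Dose Date - 1 for subjects receive OLTE IP dose". Table 2 ends the Week 12 efficacy interval at "Week 12 IP dose date-1".

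On the schedule, SAP 2.4.1 puts the double-blind doses "at Day 1 and Weeks 4 and 8", and protocol 5.5.4 puts the open-label doses "at Weeks 12, 16, 20, 24, etc". The Week 12 dose is therefore the first open-label dose. Protocol 5.5.4 allows 5 days either side of each 4-week point, counted from the first dose. SAP 2.7.7 summarizes exposure duration in days by treatment group and by phase.

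**The concern.** All three formulas end in +1, so both end dates are counted. If the first open-label dose date is the smallest term in the first formula, that date is a day of double-blind exposure. The third formula also counts it, as day 1 of open label.

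The subtraction of 1 sits on the end-of-study date, where the other two formulas have none. It is missing from the first open-label dose date, where Tables 2 and 4 have it. That pattern points to a misplaced term. What is at stake is the accuracy of the planned exposure summary, and whether a programmer following the formula literally would obtain durations that fit the rest of the section.

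**Working it through.** The documents state no numerical result for this formula, so there is no figure to reproduce. The check evaluates the printed rule in study days, with the first double-blind dose on day 1.

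**Inputs**
- L = last double-blind dose (Week 8): target day 57, window days 52 to 62.
- F = first open-label dose (Week 12): target day 85, window days 80 to 90.
- E = end-of-study date, defined in SAP 2.1.3 as the patient's last date in the study. For a patient who receives an open-label dose, E is on or after F.

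**Formulas**
- As printed: double-blind days = MIN(L + 27, F, E − 1) − 1 + 1 = MIN(L + 27, F, E − 1).
- Corrected: MIN(L + 27, F − 1, E) − 1 + 1 = MIN(L + 27, F − 1, E).
- Open-label exposure starts on day F, so a day is shared when the last double-blind day is F.

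**Results, with E well after F**

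| L | F | Gap F − L | Printed | Corrected | Shared days |
|---|---|---|---|---|---|
| 57 | 85 | 28 | 84 | 84 | 0 |
| 57 | 86 | 29 | 84 | 84 | 0 |
| 57 | 84 | 27 | 84 | 83 | 1 |
| 57 | 83 | 26 | 83 | 82 | 1 |
| 57 | 80 | 23 | 80 | 79 | 1 |
| 62 | 85 | 23 | 85 | 84 | 1 |
| 52 | 90 | 38 | 79 | 79 | 0 |

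**When it happens.** F is counted as double-blind exactly when F ≤ L + 27, that is, at a gap of 27 days or fewer. At 28 days or more, L + 27 falls before F and there is no overlap. The trigger is the gap and not an early Week 12 dose alone: the row with L = 62 and F = 85 has an on-time Week 12 dose after a late Week 8 dose. The overlap is never more than one day, and 1/84 = 1.2%.

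**What the subtraction does where it stands.** E − 1 is smaller than F only if E = F, meaning that the patient's last day in the study is the first open-label dosing day. With L = 57 and F = E = 82, both versions give 81 days and nothing is shared. In every other case the term is inert.

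**How often.** The window allows 11 × 11 = 121 date combinations. Overlap needs the Week 12 offset to be smaller than the Week 8 offset: 11 × 10 / 2 = 55 combinations. This counts combinations and does not estimate a share of patients.

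A share needs a distribution of offsets, which the documents do not give. If the two offsets are independent with the same distribution, the share is (1 − probability that they are equal) / 2.
- Uniform over ±5 days: (1 − 1/11) / 2 = 0.455.
- Normal, SD 1 day, rounded to whole days: probability of equality about 0.271; share (1 − 0.271) / 2 = 0.36.
- Normal, SD 0.5 day, rounded: probability of equality about 0.516; share (1 − 0.516) / 2 = 0.24.

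Each affected patient contributes one day, so the mean overstatement in days among patients who roll over equals the share.

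**After the correction**, none of the 121 combinations overlaps, and the on-schedule patient stays at 84 days.

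**The case against.** The best case on the other side accepts the arithmetic and disputes its reach. Most of it stands.

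- **Frequency.** A reader might infer that some 36% to 45% of patients are affected, with a mean overstatement of about 0.4 day. The documents do not support that. Those values rest on assumed offsets, and the lower one is not a floor: an SD of half a day gives 24%. Section 6 of the protocol asks for visits on the planned day or as near to it as possible, which favours exact 28-day gaps. Patients who keep the same weekday throughout would lower the share further.
- **Table 4.** A reader might take disagreement with Table 4 as proof of error. By itself it is not. Table 4 is a safety reporting window and differs from exposure by design: without open label it can run to last dose + 84 days, while exposure stops at + 27. For gaps over 28 days, exposure also ends before the Table 4 phase does. The stronger evidence is within the exposure formulas: the open-label formula begins on the contested day, and neither sibling formula subtracts 1 from the end-of-study date. Tables 2 and 4 support only the convention that the double-blind period ends the day before the first open-label dose.
- **Table 3.** Its Week 12 visit window includes the open-label dose date. That concerns assessments made before dosing and does not justify counting the day as double-blind exposure.
- **Adverse event rates and efficacy.** A reader might infer that exposure-adjusted incidence is biased. It is not affected: SAP 2.1.1 takes time at risk from the safety window, which for these patients ends the day before the first open-label dose. Table 2 does the same for efficacy.
- **Total exposure.** The two durations can add up to more than elapsed time, but the documents plan no such sum. SAP 2.7.7 reports by phase, and SAP Section 1 leaves the open-label analysis to a separate plan.
- **Comparison of arms.** One formula and one schedule serve both arms, so no difference between arms is shown.

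What does not fall is the core: the printed rule gives a duration that is one day too long in a planned table whenever the gap is 27 days or fewer.

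**Conclusion.** Wrong as written, and minor. Double-blind exposure is overstated by exactly one day (about 1.2% of 84 days) for each patient whose first open-label dose comes 27 days or fewer after the last double-blind dose, apart from the rare patient whose study ends on that dosing day. The error goes in one direction only.

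This follows from the printed formulas and needs no assumption beyond reading OLTP as OLTE. That the subtraction was put on the wrong term is an inference, though a well-supported one. The number of patients affected is unknown from the documents, and the 24% to 45% range is illustrative. The consequence is confined to the descriptive exposure summary.

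**What to change.** In SAP 2.1.1, for patients who enter open label, define double-blind exposure as: Minimum (Last DB Dose Date + 27, First OLTE Dose Date − 1, EoS Date) − First DB Dose Date + 1. Write OLTE instead of OLTP. The other two exposure formulas and Tables 2 and 4 stay as they are.

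The cost is one formula in the SAP and the matching line in the program. No data collection, test or other derivation changes. If the exposure table has already been produced, it needs to be rerun.

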7.3 Liver safety monitoring

To ensure patient safety and enhance reliability in determining the hepatotoxic potential of an investigational drug, a standardized process for identification, monitoring and evaluation of liver events has to be followed.

The following two categories of abnormalities/adverse events have to be considered during the course of the study (irrespective of whether classified/reported as (S)AE):

- Liver laboratory triggers, which will require repeated assessments of the abnormal laboratory parameter
- Liver events, which will require close observation, follow-up monitoring and completion of the standard base liver eCRF pages

Please refer to [Table 13-1-Appendix 2](#) for complete definitions of liver laboratory triggers and liver events.

Every liver laboratory trigger or liver event as defined in [Table 13-1-Appendix 2](#) should be followed up by the investigator or designated personal at the trial site as summarized below. Detailed information is outlined in [Table 13-2-Appendix 2](#).

For the liver laboratory trigger:

- Repeating the liver function test (LFT) within the next week to confirm elevation.

These LFT repeats must be performed using the central laboratory if possible. If this is not possible, then the repeats can be performed at a local laboratory to monitor the safety of the patient. Repeats laboratory must then be performed at central laboratory as soon as possible. If a liver event is subsequently reported, any local LFTs previously conducted that are associated with this event must be reported on the Liver eCRF pages.

- If the elevation is confirmed, close observation of the patient will be initiated, including consideration of treatment interruption if deemed appropriate.

For the liver events:

- Repeating the LFT to confirm elevation as appropriate
- Discontinuation of the investigational drug if appropriate
- Hospitalization of the patient if appropriate
- A causality assessment of the liver event via exclusion of alternative causes (e.g., disease, co-medications)
- An investigation of the liver event which needs to be followed until resolution.

These investigations can include serology tests, imaging and pathology assessments, hepatologist's consultancy, based on investigator's discretion. All follow-up information, and the procedures performed must be recorded on appropriate eCRF pages, including the liver event overview eCRF pages.

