2.7.2 Laboratory data

Summary statistics will be presented for absolute as well as change from baseline of laboratory haematology, blood chemistry results over time by treatment and laboratory test category.

Summary of change from baseline for absolute neutrophil count (ANC), alanine transaminase (ALT) and aspartate aminotransferase (AST) will also be provided for entire study.

Additional liver test summary table will provide the number and percentage of subjects by following categories:

- AST and ALT ($> 3x$ ULN; $> 5x$ ULN; $> 10x$ ULN; $> 20x$ ULN respectively)
- ALT/AST $> 3x$ ULN and Total Bili $> 2x$ ULN and ALP $\leq 2x$ ULN
- ALT/AST $> 3x$ ULN and Total Bili $> 2x$ ULN and ALP $> 2x$ ULN

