2.7.5 Vital signs

The analyses of vital signs (systolic/diastolic blood pressure, pulse rate, and weight) will include summary statistics of change from baseline over time separately for DBTE by treatment group.

Summaries will be provided at each time-point for subjects meeting the following defined categories:

- Change from baseline: ≥ 15 mmHg in diastolic blood pressure and/or ≥ 20 mmHg in systolic blood pressure and analyzed for systolic blood pressure (< 90 mmHg, > 180 mmHg) and diastolic blood pressure (< 50 mmHg, > 105 mmHg)
- Change from baseline in heart rate of ≥ 15 bpm (ie, an increase of at least 15 bpm) or heart rate > 120 bpm
- Change from baseline in heart rate of ≤ -15 bpm (ie, a decrease of at least 15 bpm) or heart rate < 50 bpm

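### Vital-sign limit counts and by-visit laboratory tables can miss off-schedule safety readings, and the liver threshold table does not state which readings it uses

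*SAP*

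**What the plan says.** SAP 2.1.1, under Analysis windows, states that "by-visit analyses, including evaluable scheduled and unscheduled data, will be conducted using analysis windows". Where several safety readings share a window, one is kept: "For safety parameters: in case of competing assessments within a analysis window, the last one closest to the scheduled visit day will be used". The preceding paragraph, on efficacy parameters, deals with an early-withdrawal reading that competes with another: "In such cases the early-withdrawal assessment will be used". The safety rule has no such sentence.

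The general construction rule is that windows "have its lower and upper bounds symmetrically between the analysis window midpoints (i.e. the scheduled visit day for the particular assessment". Table 3 then fixes the windows for vital signs and C-SSRS: Day 1, Days 16-43 (Week 4), Days 44-71 (Week 8) and Day 72 onward (Week 12). Its column header restricts laboratory tests: "include only Day1, Week 12, 24, 64". Table 4 gives a separate window covering the double-blind epoch, for safety analyses summarized by study phase.

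Two sets of threshold tables depend on these choices. For vital signs, SAP 2.7.5 says: "Summaries will be provided at each time-point for subjects meeting the following defined categories". For liver tests, SAP 2.7.2 says: "Additional liver test summary table will provide the number and percentage of subjects by following categories". It names no visit, phase or worst-value basis.

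Off-schedule samples are foreseen. Protocol 5.6.2 asks for the final-visit assessments when a patient leaves early, and Table 6-1 marks chemistry and hematology at the combined Week 12 and early-discontinuation visit. For a liver laboratory trigger, Protocol 7.3 requires "Repeating the liver function test (LFT) within the next week to confirm elevation".

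**The concern.** Threshold tables exist to find patients who crossed a limit at any time. Keeping the reading nearest the target day suits a mean-change table, but in a threshold table it can replace an abnormal reading with a normal one from the same window. Unscheduled and repeat readings are often taken because something looked wrong, so leaving them out would tend to lower the counts, and more so in an arm with more triggered visits or early stops. For laboratory tests, a patient whose only on-treatment sample was drawn at an early-termination visit before Day 72 would have no post-baseline value in any by-visit table.

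**Working it through.** **1. Reproduce the stated windows.** Target days in Table 3 are 1, 29, 57 and 85; the next 4-weekly day is 113. The midpoints are (1+29)/2 = 15, (29+57)/2 = 43, (57+85)/2 = 71 and (85+113)/2 = 99. Windows starting the day after each midpoint are 16-43, 44-71 and 72-99, which match Table 3.

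**2. Days without a window.** Table 3 sets the Day 1 window to Day 1 only.
- Vital signs: Days 2-15 have no window, 14 days.
- Laboratory tests: only the Day 1 and Week 12 rows apply in the double-blind epoch, so Days 2-71 have no window, 70 days.

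**3. Apply the midpoint rule to the laboratory schedule.** With scheduled days 1 and 85 the midpoint is (1+85)/2 = 43, so the Week 12 laboratory window would start on Day 44, not Day 72. That recovers Days 44-71 (28 days). Days 2-43 would still have no window while Day 1 stands alone.

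**4. Apply the selection rule to illustrative days** (smallest distance to target; the last if tied).

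| Readings | Target | Distances | Kept |
|---|---|---|---|
| Vital signs, Days 29 and 40 | 29 | 0, 11 | Day 29 |
| Vital signs, Day 40 only | 29 | 11 | Day 40 |
| Vital signs, Days 26 and 32 | 29 | 3, 3 | Day 32 |
| Laboratory, Days 79 and 84 | 85 | 6, 1 | Day 84 |

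In the first row, an abnormal early-termination reading on Day 40 is not counted if the Day 29 reading was normal. In the second row, the same reading is counted because nothing competes with it. The fourth row (a patient with no open-label dose before Day 84) shows that a normal repeat can displace the raised value that prompted it, in any table using this rule.

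**5. Which samples fall on Days 2-71.** Table 6-1 schedules no chemistry between Day 1 and Week 12. Laboratory samples on those days are early-termination, repeat or unscheduled ones.

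**6. Bound on early stops.** The Amendment 3 rationale in the Protocol reports 246 randomized, 242 completing the double-blind epoch and 240 continuing to open label. Protocol 3.1 admits to open label only patients who completed on study drug. If that rule was followed, early stops of study drug number at most 246 - 240 = 6, and 6/246 = 2.4%. Non-completers of the epoch number 246 - 242 = 4, and 4/246 = 1.6%. Neither document gives a count of unscheduled or repeat tests.

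**The case against.** The strongest reply is that most of the safety reporting does not depend on these windows. Table 4 spans the double-blind epoch, C-SSRS is summarized by maximum severity (2.7.3), listings hold every assessment, and clinically significant laboratory abnormalities are adverse events under Protocol 7.1, so they reach the adverse-event and withdrawal tables. No safety comparison is tested. All of this stands. However, listings do not give counts by arm, and an adverse-event entry depends on the investigator's judgment, whereas a threshold count does not.

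Three stronger readings are tempting, and the documents do not support them.
- A reader might infer that ALT/AST peaks or potential Hy's law cases will be dropped from the liver table. The closest-value rule is written for by-visit analyses and 2.7.2 names no visit, so a phase-level count under Table 4 is at least as natural. The basis is unstated; loss is not shown.
- A reader might infer that all off-schedule readings are lost. Unscheduled data are expressly eligible, and inside a window they are kept when they are the only or closest value. The rule also ignores the result, so it can retain the abnormal reading.
- A reader might take 70 of 84 days (83%) as the share of laboratory data lost. It is a share of days on which no laboratory draw is scheduled.

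Two further points reduce the weight of the laboratory limb. A repeat liver test on Days 2-71 can follow only a Day 1 sample or an unscheduled one. The midpoint rule is introduced as general, with detail left to the tables, and part of the Table 3 header is blacked out, so the reading rests on its visible words.

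**Conclusion.** The point holds in a limited form. Followed as written, the vital-sign limit counts can miss an abnormal off-schedule reading in two situations: another reading in the window is closer to target, or the reading falls on Days 2-15. By-visit laboratory tables omit any sample on Days 2-71, and the Day 72 start departs from the SAP's own midpoint rule. For the liver threshold table the established defect is an unstated basis, which lets two programmers produce different counts.

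The effect is probably small: at most about 6 early stops among 246 patients, assuming open-label entry followed Protocol 3.1, plus an unknown number of unscheduled or repeat tests. No efficacy result is affected. The change is still worth making, because limit crossings are rare enough for one missed patient to matter and the data are already collected. The SAP already uses the epoch maximum for C-SSRS.

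**What to change.** - In SAP 2.7.2 and 2.7.5, base the threshold tables (ALT/AST multiples, combined ALT/AST-bilirubin categories, blood pressure and pulse limits) on the worst value among all post-first-dose assessments in the Table 4 double-blind window: scheduled, unscheduled, repeat and early-termination. Blood pressure and pulse have limits in both directions, so use both the highest and the lowest value. State whether the combined liver categories need values from the same sample.
- When applying Table 4, include pre-dose readings on the day of the first open-label dose. Table 4 closes the day before, while the Table 3 Week 12 window includes that day. Without this, the scheduled Week 12 sample of patients who continue could be excluded.
- Keep the closest-value rule for mean change over time only.
- In Table 3, assign early-termination laboratory samples to a post-baseline time point, and either align the Week 12 laboratory window with the midpoint rule or state the exception.

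The cost is a few sentences in the SAP and minor programming. Counts of notable values may be slightly higher.
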